# Safety

# **Primary Safety Parameters**

The primary safety parameter is the incidence of patellar fracture, dislocation, subluxation and wear.

### **Secondary Safety parameters**

The secondary safety parameter is the incidence of all other device related adverse events.

# **Primary Safety Hypothesis**

The incidence of patellar fracture, dislocation, subluxation and wear is the same in the Triathlon CR group as in other commercially available knees.

# **Secondary Safety Hypothesis**

The incidence of all other device related adverse events is the same in the Triathlon CR group as in other commercially available knees.

# **Missing Data**

Scores for missing SF-12 data will be imputed using the SF Health Outcomes Scoring Software. Both raw and imputed results will be reported. The imputed values will be analyzed.

# **Statistical Methodology**

#### **Data Summary**

All data entry and analysis will be done by the Mayo Clinic Division of Biostatistics.

The following is a detailed proposal of statistical analyses planned for data collected during the study. In general, data will be summarized by treatment group and nominal study visit, where applicable.

For parameters represented by continuous variables (e.g., ROM), the summaries will consist of the mean, median, standard deviation, minimum, and maximum values. Both the actual values at each nominal visit and the improvement from baseline at each post-baseline visit for each treatment group and their difference will be presented with its 95% confidence intervals. The improvement from baseline will also present the corresponding paired t-test p-values.

For categorical variables (e.g., subsidence), the number of events, person-years of follow-up, and the corresponding event rates with 95% confidence intervals will be presented.

In addition, the rate ratios (relative risk) of the treatment groups along with 95% confidence intervals will be presented.

Descriptive statistics and statistical comparisons for important demographic, efficacy, and safety variables will be provided in tables. All data collected on the case report forms will be provided in data listings, which will be sorted by treatment group and patient number.

Documentation of statistical analyses will be provided in a statistical appendix. All statistical analyses will be completed using SAS®, version 9 or higher (SAS Institute Inc,

Cary, NC), and Splus, version 7 or higher (Insightful Corporation, Seattle, WA).

All statistical tests will be two-sided and p-values less than 0.05 will be considered

significant.

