#### STATISTICAL METHODS AND REVIEW STATEMENT

#### **Primary Efficacy Parameters**

The primary efficacy parameter is the revision rate for total knee arthroplasty. The key time point is ten years post-surgery.

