### **Secondary Efficacy Parameters**

The secondary efficacy parameters include:

Active flexion, Passive flexion, Active extension, and Passive extension ROM at the 2, 5, 7 and 10-year visits.

KSS pain and motion scores at the 3 months, 2, 5, 7 and 10-year visit.

SF-12 scores at the 3 months, 2, 5, 7 and 10-year visit.

Radiographic success/failure at the 3 months, 2, 5, 7 and 10-year visits.

Radiographic failure is defined as a score of 10 or greater according to the Knee Society

Rotenographic Scoring System, regardless of symptoms. A migrating or shifting

prosthesis with or without the disappearance of radiolucent lines is also a failure

regardless of the score.

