**Secondary Efficacy Hypothesis** 

For the secondary efficacy parameters (when data is available), a non-inferiority

hypothesis will be tested at each scheduled follow-up visit, similar to the primary efficacy

hypothesis.

In addition, a comparison of the scores at each post-surgery visit with baseline (i.e.,

improvement scores) will be tested to see if any improvement is seen for each parameter

and time point.

For categorical secondary parameters (i.e., radiographic success/failure, subsidence and

radiolucency), the non-inferiority alternative hypothesis is that the risk in the X3

polyethylene group is not  $\Delta_0$ % worse relative to the N2Vac treated group within the

period from surgery to the scheduled follow-up visit. Formally the non-inferiority null

and alternative hypotheses are:

 $H_{NI,O}$ :  $\pi_{X3}/\pi_{N2Vac} > \Delta_0$ , and

 $H_{NI,A}$ :  $\pi_{X3}/\pi_{N2Vac} < \Delta_0$ , where  $\pi_{X3}$  is the rate in the Triathlon CR Total Knee

System group using the X3 polyethylene,  $\pi_{N2Vac}$  is the rate in the Triathlon CR

Total Knee System group using the N2Vac, and  $\Delta_0$  is the equivalence limit

difference ( $\Delta_0$ ).

For continuous secondary parameters (i.e., ROM, KSS, SF12), the non-inferiority

alternative hypothesis is that the mean using the X3 polyethylene is not  $\Delta_0$  worse than the

mean using the N2Vac treated group within ten years. Formally the non-inferiority null

and alternative hypotheses are:

 $H_{NI,O}$ :  $\mu_{X3} \ge \mu_{N2Vac} + \Delta_0$ , and

 $H_{NI,A}$ :  $\mu_{X3} < \mu_{N2Vac} + \Delta_0$ , where  $\mu_{X3}$  is the mean in the Triathlon CR Total Knee System group using the X3 polyethylene,  $\mu_{N2Vac}$  is the mean in the Triathlon CR Total Knee System group using the N2Vac, and  $\Delta_0$  is the equivalence limit difference ( $\Delta_0$ )..

The equivalence limit differences are as follows.:

Parameter	Equivalence Limit Difference ( $\Delta_0$ )
Range of Motion (ROM)	10 degrees
KSS pain and motion	10%
SF-12	10%
Radiographic success/failure	No complete radiolucent lines
Subsidence and Radiolucency	No component subsidence

In addition, for the continuous parameters, a comparison of the scores at each postsurgery visit with baseline (i.e., improvement scores) will be tested to see if any improvement is seen for each parameter at each time point. That is, the formal hypothesis to be tested is that the difference is zero. This is tested by:

$$H_{I,O}$$

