# **Efficacy Analyses**

#### Methods

Primary Parameter: The relative risk of revision (X3 relative to N2Vac) at ten years will be computed and a 95% confidence interval on the rate ratio computed, assuming a Poisson distribution. If the upper end of the confidence interval for the rate ratio is less than 1.0, then the superiority hypothesis will be supported. Otherwise, if the upper end of the confidence interval is less than 1.2, then the non-inferiority hypothesis will be supported. Secondary Parameters: The categorical secondary efficacy parameters will be analyzed at each nominal visit by computing the 95% confidence interval for the rate ratio (relative risk) of the groups as above. The clinically significant difference ( $\Delta_0$ ) is as presented on page 13 above. The continuous secondary efficacy parameters will be analyzed at each nominal visit. The 95% confidence interval on the difference between the two groups will be computed using the means, t-distribution and appropriate standard deviation. The change from baseline will also be presented and their 95% confidence interval and p-value for the paired t-test using the baseline will be presented for each nominal visit and treatment group, along with the descriptive statistics.

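### Secondary non-inferiority is tested at every visit with no order, key visit or adjustment, so the familywise error rate of the secondary claims is uncontrolled

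*Combined protocol and SAP*

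**What the plan says.** Secondary Efficacy Hypothesis states that, for the secondary parameters, a non-inferiority "hypothesis will be tested at each scheduled follow-up visit, similar to the primary efficacy" hypothesis. Secondary Efficacy Parameters lists what is tested and when:

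- Range of motion, with four measures: "Active flexion, Passive flexion, Active extension, and Passive extension ROM at the 2, 5, 7 and 10-year visits".
- The Knee Society score, at one visit more than range of motion: "KSS pain and motion scores at the 3 months, 2, 5, 7 and 10-year visit".
- General health, on the same five-visit schedule: "SF-12 scores at the 3 months, 2, 5, 7 and 10-year visit".
- Radiographic success or failure, also at those five visits.

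Secondary Efficacy Hypothesis also treats subsidence and radiolucency as categorical secondary parameters.

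The decision tools are under Efficacy Analyses, Methods. For categorical outcomes: "The categorical secondary efficacy parameters will be analyzed at each nominal visit by computing the 95% confidence interval for the rate ratio". For continuous outcomes: "The 95% confidence interval on the difference between the two groups will be computed using the means, t-distribution and appropriate standard deviation". The same section adds a paired t-test against baseline for each continuous parameter, visit and arm. Data Summary then sets the general rule: "All statistical tests will be two-sided and p-values less than 0.05 will be considered" significant.

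Two features that could have limited the testing apply to the primary parameter only. Primary Efficacy Parameters says "The key time point is ten years post-surgery", and Methods sets the order of superiority then non-inferiority for the revision rate ratio. No section gives the secondary parameters a key visit, an order, an adjustment or a descriptive label.

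**The concern.** A rule that tests everything at every visit, with each result standing alone, lets any parameter at any visit be reported as a formal conclusion. The reader of the final report would have no error rate for the set of claims and no way to tell a pre-planned conclusion from a selected one.

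The paired tests raise a separate problem. They ask whether each arm improved after knee replacement, which most patients are expected to do with either insert. They would add many significant p-values that carry no information on X3 against N2Vac.

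**Working it through.** The plan states no familywise error rate, so there is no figure of its own to reproduce. The check counts the comparisons, fixes the level of each, and works out what follows.

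**Step 1: count of non-inferiority comparisons** (parameters × visits, from Secondary Efficacy Parameters and Secondary Efficacy Hypothesis). The plan does not say whether KSS pain and motion are one score or two, or how many SF-12 scores are analysed, so both readings are shown.

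| Parameter | Visits | Narrow | Wide |
|---|---|---|---|
| ROM, 4 measures | 4 | 16 | 16 |
| KSS pain and motion, 1 or 2 scores | 5 | 5 | 10 |
| SF-12, 1 or 2 scores | 5 | 5 | 10 |
| **Subtotal with a numeric limit** | | **26** | **36** |
| Radiographic success/failure | 5 | 5 | 5 |
| Subsidence and radiolucency, not counted or 2 | 5 | 0 | 10 |
| **Total** | | **31** | **51** |

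The last two parameter rows have no numeric limit: the table of equivalence limits gives a verbal condition for each. These 5 to 15 comparisons cannot be run as non-inferiority tests as written. The calculation below therefore uses 26 to 36. Safety parameters and complications are not in the count.

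**Step 2: level of each comparison.** Non-inferiority is read from one bound of a 95% interval, so each comparison is at one-sided 0.025. The 0.05 in Data Summary is the two-sided level.

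**Step 3: worst case, independent tests.** If X3 is truly at the limit on every one of m comparisons, P(at least one false claim) = 1 − 0.975^m.

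- m = 26: 1 − 0.975^26 = 0.48; expected false claims 26 × 0.025 = 0.65
- m = 36: 1 − 0.975^36 = 0.60; expected false claims 36 × 0.025 = 0.90

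**Step 4: worst case, correlated tests.** Visits and related scores are correlated, and the documents give no correlations. The values here are assumptions, run as a normal simulation with 200,000 draws.

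| Correlation within / between parameters | m = 26 | m = 36 |
|---|---|---|
| 0.5 / 0.2 | 0.34 | 0.41 |
| 0.6 / 0.3 | 0.29 | 0.35 |
| 0.7 / 0.4 | 0.25 | 0.30 |

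As a stronger case, a single common correlation of 0.8 across 36 tests gives 0.14. Every value is above 0.025.

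**Step 5: within-arm tests.** One paired test per continuous parameter, visit and arm gives 26 × 2 = 52 to 36 × 2 = 72. With 286 × 0.9 ≈ 257 patients per arm, a true change of 0.3 SD has power Φ(0.3 × √257 − 1.96) = Φ(2.85), over 99%. These tests will be significant after even a modest true improvement, whichever insert was used.

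**Step 6: effect of limiting formal claims to ten years.** The comparisons with a numeric limit fall to 4 ROM + 1 or 2 KSS + 1 or 2 SF-12 = 6 to 8. Without an order, the worst case if independent is 1 − 0.975^6 = 0.14 to 1 − 0.975^8 = 0.18. With a fixed order that stops at the first failure, it is 0.025.

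**The case against.** The strongest reply is that the percentages describe an extreme case. A false non-inferiority claim needs a true difference at or beyond the limit. If the two inserts perform equally, every non-inferiority claim is true. That stands, so a reader who infers that some secondary claims will be chance findings goes further than the documents allow. What remains is that, under Data Summary, a between-arm difference with p below 0.05 at any visit would still be called significant. The plan states no superiority hypothesis for the secondary parameters, so no probability is attached to that here.

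Three other strong readings also fail. It is tempting to say each non-inferiority comparison is made at 0.05, but the interval rule makes it one-sided 0.025. It is tempting to say no secondary result has an error rate, but each comparison with a numeric limit has its own nominal rate and only the familywise rate is missing. And the paired tests might be counted as a source of chance findings, but improvement after knee replacement is expected, so those results would mostly be true. The objection to them is that they do not compare the arms.

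It is also fair to say that the plan already has part of the remedy: Data Summary presents the between-arm difference in improvement with a 95% interval.

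Finally, a reader might infer that the secondary tests should wait for primary superiority. The documents do not support that. The primary hypothesis is joint superiority/non-inferiority, and such a gate would bar the secondary tests after a non-inferiority success. It would also often stay shut. At the rates in Sample Size Justification, 260 × 0.05 + 260 × 0.016 = 13 + 4.2, about 17 revisions. Schoenfeld power is then Φ(√17/2 × |ln 0.32| − 1.96) ≈ 0.65, so the gate would fail about one time in three under the plan's own assumed effect.

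None of this supplies an order, a key visit, an adjustment or a descriptive label for the secondary claims.

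**Conclusion.** The concern holds as a lack of familywise control over the secondary claims. The plan has an explicit rule to test at every visit and to call results significant one by one, so this is more than missing detail. The primary analysis is unaffected: it has one endpoint, one interval and no interim analysis.

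The 48-60% (independent) and 25-41% (correlated) figures are upper bounds on the problem. They rest on X3 lying exactly at the limit on every testable comparison, on the one-score or two-score readings of KSS and SF-12, and on correlations that are assumed. They show that the familywise rate can be far above 2.5%; they do not predict what this trial will find.

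**What to change.** In Secondary Efficacy Hypothesis, Data Summary and Efficacy Analyses, Methods:

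1. Limit formal secondary claims to the ten-year visit, for parameters with a usable numeric limit. The 10% for KSS and SF-12 needs a stated base before those parameters qualify.
2. Write down one testing order before analysis. Test in that order at the existing level (one bound of the 95% interval) and stop at the first failure. Do not make this depend on primary superiority. The control then applies within the secondary family, separately from the primary test.
3. Report all other visits and parameters as estimates with 95% intervals, with no claim of significance or non-inferiority.
4. Drop the within-arm paired p-values and rely on the between-arm difference in improvement with its interval, which Data Summary already provides.

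This is a change of SAP wording only; enrolment, visits and data collection stay as they are. The cost is that fewer results may be called significant, and an early failure in the order closes the parameters after it. All estimates are still shown.

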**Sample Size Justification** 

Revision rates for total knee arthroplasty are approximately 0.5% per year over the life of

the knee. At ten years, this rate would be expected to be 5%. Within the Triathlon PS,

X3 has been shown to reduce wear over N2Vac by up to 68%. Therefore, by assuming

all revisions could be attributed to polyethylene debris the X3 can be assumed to have a

revision rate of 1.6% at 10 years. Assuming that the X3 knees have a 10-year revision

rate of 1.6% and that the corresponding rate in the N2Vac knees is 5.0% yields a rate

ratio of 0.32 (or 3.1 for N2Vac/X3). In order to have 80% power to detect this rate ratio

as being significantly different from 1.00 will require that 26 events (revisions) are

observed during the 10-year follow-up period. Assuming the overall 10-year revision rate

is 5%, the sample size required to observe 26 revisions is 26/0.05=520, or n=260 in each

treatment group. By factoring in a 10% lost to follow-up rate within the ten-year period,

the total enrollment of about 572 subjects (286 in each group) will be needed.

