#### **RISKS**

Participation in this study, involving FDA-approved devices, poses no increased risk to patients undergoing total knee replacement surgery. With any knee replacement, there is a possibility that the prosthesis will need to be removed and replaced and that the procedure may involve unforeseeable risks. Some of the known risks include: failure to achieve firm attachment of the implant to the bone, fracture of bone during implantation, infection, deep vein thrombosis, neurovascular injury, wound problems, extensor mechanism problems, and anesthetic problems. In a minority of cases, the knee prosthesis will loosen over years of use and pain and decreased mobility will occur.

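### The rate ratio of 0.32 applies the maximum wear reduction to revisions of every cause, and no analysis of insert-related revision is planned that would help interpret a null result

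*Combined protocol and SAP*

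**What the plan says.** The Sample Size Justification starts from an annual revision rate of about 0.5% and cumulates it: "the knee. At ten years, this rate would be expected to be 5" per cent. It then states that "X3 has been shown to reduce wear over N2Vac by up to 68" per cent, and supposes that "all revisions could be attributed to polyethylene debris the X3 can be assumed to have a" "revision rate of 1.6% at 10 years". The resulting design target is a rate "ratio of 0.32 (or 3.1 for N2Vac/X3). In order to have 80% power to detect this rate ratio", with 26 revisions required. No wear-related share of revisions, range of effects or supporting argument is given.

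The endpoint is not restricted by cause. Under Primary Efficacy Parameters, "The primary efficacy parameter is the revision rate for total knee arthroplasty", and Efficacy Analyses compares all revisions through a Poisson rate ratio with a 95% interval.

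The Risks section says that a prosthesis may have to be taken out and exchanged, and then lists known risks that include "failure to achieve firm attachment of the implant to the bone, fracture of bone during implantation, infection, deep vein thrombosis". The Complications/Lost to Follow-up Form section also names sepsis and fracture. Neither Secondary Efficacy Parameters nor Efficacy Analyses contains an analysis of revision by cause.

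**The concern.** The rationale for X3 is less wear debris. It predicts a change only in the revisions that debris causes. If some N2Vac revisions have other causes, and those occur equally in both arms, the all-cause ratio moves towards 1 and power falls. The planned effect of 0.32 combines two favourable extremes: the maximum wear reduction, and a 100% debris share.

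The practical stake is the reading of the result after ten years. If the all-cause interval includes 1, the planned revision analysis could not readily tell an absent wear benefit from one masked by revisions for infection or fracture. Grouping causes after the data are known would be post hoc.

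**Working it through.** **Inputs.** From Sample Size Justification: N2Vac 5% at ten years, wear reduction 68% (a maximum), 26 events, 520 evaluable, 10% loss, 286 enrolled per arm. From Data Summary: "All statistical tests will be two-sided and p-values less than 0.05 will be considered" significant. Assumed: a share s of N2Vac revisions is wear-related, and other revisions are equally frequent in both arms.

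**The plan's own figures.** 5% × (1 − 0.68) = 1.6%, and 1.6/5.0 = 0.32. The plan names no formula for 26 events. Schoenfeld's gives 4 × (1.960 + 0.842)² / (ln 0.32)² = 24.2, so 25, and power of 82.8% at 26 events. The figure is therefore reproduced approximately. Then 26/0.05 = 520, and 520 × 1.10 = 572.

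**Effect of the share.** All-cause ratio = [s × 0.32 + (1 − s)] / 1 = 1 − 0.68s:
- s = 75%: 1 − 0.51 = 0.49
- s = 50%: 1 − 0.34 = 0.66

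**Same formula, 26 events held.** Power is 82.8% at s = 100%, 67.5% at 90% (ratio 0.388), 44.4% at 75% and 18.4% at 50%. Events needed for 80% power are 25, 36, 62 and 182. If s = 100% but the wear reduction is 50% (assumed), the ratio is 0.50, power is 42.4% and 66 events are needed.

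**Power under the plan's decision rule.** Both revision counts are taken as independent Poisson, and power is the total probability of all pairs of counts whose upper 95% limit is below 1. The Wald limit is exp[ln(b/a) + 1.96 √(1/a + 1/b)], where a is the N2Vac count and b the X3 count, with 0.5 added to both when either is zero. The exact version is conditional on a + b. Evaluable per arm: 286 × 0.90 = 257.4, so the N2Vac mean is 257.4 × 0.05 = 12.87.

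| s | All-cause means (N2Vac, X3) | All-cause power, Wald (exact) | Wear-specific means (N2Vac, X3) | Wear-specific power, Wald (exact) |
|---|---|---|---|---|
| 100% | 12.87, 4.12 | 54% (49%) | same | same |
| 75% | 12.87, 6.31 | 29% (25%) | 9.65, 3.09 | 37% (35%) |
| 50% | 12.87, 8.49 | 14% (11%) | 6.44, 2.06 | 15% (20%) |

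**Holding 26 total revisions**, with N2Vac mean 26/(1 + ratio):

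| s | All-cause means (N2Vac, X3) | All-cause power, Wald (exact) | Wear-specific means (N2Vac, X3) | Wear-specific power, Wald (exact) |
|---|---|---|---|---|
| 100% | 19.70, 6.30 | 76% (70%) | same | same |
| 75% | 17.45, 8.55 | 40% (34%) | 13.09, 4.19 | 55% (50%) |
| 50% | 15.66, 10.34 | 17% (13%) | 7.83, 2.51 | 25% (27%) |

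**Separating two causes of the shortfall.** At s = 100% there is no dilution, yet power is 54% (49%). The plan uses 5% as the overall rate, but 5% and 1.6% average 3.3%, so 520 evaluable patients yield 520 × 0.033 = 17.2 expected revisions, not 26. That is a separate problem. Dilution accounts for the fall from 54% to 29% or 14%.

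**The case against.** - **The assumption is disclosed.** The plan says that it attributes all revisions to debris. This stands: it is an untested best case, not a hidden or arithmetical error, and the size of the loss depends on a share that the documents do not give.
- **The Risks section does not list causes of revision.** This stands too. A reader might infer that the protocol itself contradicts the 100% share, but the list is of known risks of knee replacement, some of which (deep vein thrombosis, anaesthetic problems) are not reasons to revise. The same section also mentions loosening over years of use. What remains is that infection and fracture plausibly lead to revision.
- **All-cause revision is the right primary.** The Introduction records concern about how highly cross-linked polyethylene, in its first generation, stands up to shear in the knee. X3 could therefore add mechanical failures, which an all-cause count captures and a narrow wear count would miss. This stands: it supports the primary endpoint, makes equal non-wear revision an assumption, and means that insert breakage belongs in any insert-related category.
- **Wear is not ignored.** Radiographic failure, subsidence, radiolucency and a primary safety parameter that includes wear are to be compared by rate ratio. These help interpretation, but none is revision for an insert-related cause.
- **A cause-specific analysis does not rescue power.** At the planned size, Wald power rises from 29% to 37% at s = 75% and from 14% to 15% at s = 50%. With about 6 against 2 expected events, the Wald figure is also unreliable. A null secondary result would itself be weak evidence, so the analysis should be supportive only.

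**Conclusion.** The point holds as a matter of optimistic planning and limited interpretability. The ratio of 0.32 requires both the full 68% reduction and a 100% debris share, while the endpoint counts every revision. At the planned size, all-cause power is 29% (25%) at s = 75% and 14% (11%) at s = 50%. These figures rest on 5% in N2Vac, 257 evaluable per arm, the 68% reduction applying fully to wear-related revisions, equal non-wear revision in both arms, and an assumed s.

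A reader might infer that 80% power is reached if s is 100%. The plan's own rates do not support that: they give 54% (49%), mostly because the overall event rate is set too high. A reader might also infer that a null all-cause result would be uninterpretable. It would be hard to interpret, but the radiographic and safety comparisons give some indirect evidence.

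**What to change.** 1. Keep all-cause revision as the primary endpoint.
2. Record a coded cause for each revision, with definitions fixed in advance. The case report forms are not shown, so cause may already be collected.
3. Pre-specify, as a supportive secondary analysis, the X3/N2Vac rate ratio with a 95% Poisson interval for insert-related revision: wear, osteolysis, late aseptic loosening, and breakage or mechanical failure of the polyethylene. Keep this apart from early failure of fixation, infection, bone fracture and other causes. Define in advance how late loosening is distinguished from early fixation failure. End person-time at revision for another cause.
4. In Sample Size Justification, replace the single 80% figure with power at the planned size for s = 100%, 75% and 50%, labelling s as an assumption. Do not state that 80% is reached at s = 100%.

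The cost is at most one coded field, one further Poisson analysis and a less favourable power statement. Sample size and patient care are unchanged. The drawback is that cause is partly a judgement by surgeons who know which insert was used, and the gain in power is modest. The analysis should therefore be presented as an aid to interpretation, not as a second test of efficacy.

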# Sample Size/Inclusion Criteria

Five hundred seventy-two (572) patients will be recruited into the study; 286 receiving N2Vac polyethylene and 286 receiving X3 polyethylene.

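### With an expected 26 revisions, the Poisson interval rule for superiority has about 70% to 78% power at a rate ratio of 0.32, not the stated 80%, and the interval method is not named.

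*Combined protocol and SAP*

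**What the plan says.** The Sample Size Justification takes 10-year revision rates of 1.6% (X3) and 5.0% (N2Vac), hence a "ratio of 0.32 (or 3.1 for N2Vac/X3"). The event target follows: 80% power to find this ratio "as being significantly different from 1.00 will require that 26 events (revisions) are" seen over ten years. No formula is named. The 26 events are then converted into 520 patients and, with an allowance for loss to follow-up, 572.

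The level is set under Data Summary: "All statistical tests will be two-sided and p-values less than 0.05 will be considered" significant. Allocation is equal: "286 receiving N2Vac polyethylene and 286 receiving X3 polyethylene".

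The decision rule is under Efficacy Analyses, Methods. A 95% interval for the rate ratio is computed assuming a Poisson distribution, and "If the upper end of the confidence interval for the rate ratio is less than 1.0, then the superiority hypothesis will be supported". That section does not say whether the interval is exact, mid-P, Wald (log scale), score or likelihood-ratio.

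**The concern.** The event target and the decision rule are in different sections, and nothing shows that the 80% was calculated for that rule. With about 26 events the rule is coarse: moving one revision from one arm to the other can change the conclusion, and intervals that agree in large samples give different answers.

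Two things are at stake. First, the sample size rests on the 80%. If X3 does not reach superiority, a reader will take the chance of having missed the assumed effect as 20%, even with the full expected number of revisions. Second, because the interval is left open, a close result could be called a success or a failure according to a choice made after the data are known.

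**Working it through.** **Inputs.** Rate ratio 0.32, power 80% and 26 events (Sample Size Justification); two-sided 0.05 (Data Summary); 1:1 allocation (Sample Size/Inclusion Criteria); success if the upper 95% limit is below 1.0 (Efficacy Analyses, Methods). One assumption is added: equal person-years in the two arms.

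**1. The plan's own figure.** The usual large-sample event formula for 1:1 allocation is 4(z₀.₉₇₅ + z₀.₈₀)² / (ln RR)². With ln 0.32 = −1.139:

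4 × (1.960 + 0.842)² / 1.139² = 24.2 events.

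At 26 events the same approximation gives Φ(√26/2 × 1.139 − 1.960) = 82.8% power. So 26 is close to this formula, though not exactly its result.

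**2. The rule at a given total.** Given n revisions in all, the X3 count is Binomial(n, 0.5) under no effect and Binomial(n, 0.32/1.32 = 0.2424) under the plan's effect. At n = 26:

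| Success if X3 has | Power | One-sided error | Two-sided error |
|---|---|---|---|
| 7 or fewer | 71.7% | 0.0145 | 2.9% |
| 8 or fewer | 84.3% | 0.0378 | 7.6% |

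The interval method decides which row applies. At 8 v 18:

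- Wald: upper limit exp[ln(8/18) + 1.96 √(1/8 + 1/18)] = 1.02. Fails.
- Exact: upper limit 1.07. Fails.
- Mid-P: one-sided tail 0.0261, above 0.025. Fails.
- Score: z = (18 − 8)/√26 = 1.961, just above 1.960. Succeeds.
- Likelihood ratio: z = √{2[8 ln(16/26) + 18 ln(36/26)]} = 1.987. Succeeds.

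**3. The rule with a random total.** Enrolment and follow-up are fixed and no interim analysis is planned, so the trial does not stop at the 26th revision. Take the total as Poisson with mean 26. The expected revisions are then 26 × 0.2424 = 6.30 on X3 and 26 − 6.30 = 19.70 on N2Vac. Averaging the binomial power over the total, and the error over the same total at ratio 1.0:

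| Interval | Power, mean 26 | Average two-sided error | Approximate mean revisions for 80% |
|---|---|---|---|
| Exact | 70.2% | 3.0% | 32 (80.3%) |
| Wald | 75.6% | 4.4% | 29 (80.3%) |
| Mid-P | 75.8% | 4.5% | 29 (80.4%) |
| Score | 78.1% | 5.3% | 28 (81.0%) |
| Likelihood ratio | 78.2% | 5.3% | 28 (81.1%) |

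The Wald power is 75.4% if a zero count on X3 is treated as giving no interval. None of the five reaches 80% at a mean of 26.

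**The case against.** Planning with a large-sample event formula and analysing with a Poisson interval is routine, and such a formula comes close to 26. This stands. A reader might infer that 26 is a slip in arithmetic, but the documents do not support that. The gap is between an approximation and a discrete rule at small counts.

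A reader might also take the 71.7% at exactly 26 events as the trial's power. That is too strong, because the total is not fixed at 26 and 26 is a low point of a sawtooth. With the Wald or mid-P interval, power is 79.3% at 24 events, 75.6% at 25, 71.7% at 26, 81.3% at 27, 78.0% at 28 and 85.7% at 29. The random-total figures are the fair ones.

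Nor can the score and likelihood-ratio intervals be ruled out because their two-sided error is 7.6% at exactly 26 events. By the same test Wald and mid-P exceed 5% at 24 events (6.4%) and at 29 (6.1%). Averaged over the random total, score and likelihood ratio are at 5.3%, close to nominal, and the plan does not exclude them. With either, the shortfall is only about 2 points.

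Finally, the rates in the plan may not yield 26 revisions: 260 × 0.05 + 260 × 0.016 = 17.2. That is a separate question about converting events into patients. The present point would remain if that step were sound.

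**Conclusion.** The point holds in a moderate form. With an expected 26 revisions and a true ratio of 0.32, the written rule has about 70% power (exact), 76% (Wald or mid-P) or 78% (score or likelihood ratio). The chance of missing the assumed effect is therefore about 22% to 30%, not 20%. The direction is the same for all five intervals; the size depends on a choice that the plan leaves open. That choice also settles results such as 8 v 18.

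The figures assume equal person-years, Poisson counts and a mean total of 26. They concern superiority only and say nothing about the non-inferiority claim at 1.2.

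**What to change.** In Efficacy Analyses, Methods, name one rate-ratio interval before the data are seen. Mid-P is a reasonable choice: it is less conservative than the exact interval, and its average two-sided error is about 4.5% here.

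In the Sample Size Justification, restate the power under that interval. With mid-P the sentence could read: an expected 26 revisions give about 76% power for a rate ratio of 0.32 (mid-P interval); about 29 expected revisions are needed for 80%. The corresponding number is about 28 for score or likelihood ratio and 32 for exact.

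The cost is two sentences and a stated power lower by about 2 to 10 points, depending on the interval. This point requires no extra patients, visits or data.
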